Another study developed a new multimodal microneedle sensor array which relies on unmodified and organophosphorus hydrolase (OPH) enzyme-modified carbon paste (CP) microneedle electrodes for square wave voltammetric (SWV) detection of the fentanyl (a type of opioid) and nerve agent targets, respectively.²⁴ The patch developed in this aforementioned study is capable of continuously monitoring fentanyl down to the nanomolar level through a nanomaterial-based multilayered surface architecture.²⁴

The purpose of this study is to determine if buprenorphine, methadone, and their metabolites (i.e., norbuprenorphine [a metabolite of buprenorphine], B3G [a metabolite in buprenorphine], and EDDP [a metabolite for methadone]), can be detected in ISF. To achieve these aims, very small volumes of ISF from the surface of the skin will be collected from patients with a prescription for one of these medications using tiny needles with a standard vacuum pump. These medications and their metabolites will then be detected and quantitated in these samples using standard and well-established protocols for HPLC-MS or HPLC-MS-MS instrumental analysis for comparison to blood samples. Blood samples will be collected to compare what is in the ISF to what is in the blood. Information learned in this pilot study will be used to develop a sensor, which can be used for monitoring of these medications in humans. A continuous medication monitoring monitor could ensure safer, more effective treatment options for patients while reducing misuse, overdose, and death.

PARTICIPANT SELECTION

B. Inclusion and Exclusion Criteria: 3 groups (total n=22)

- Buprenorphine (e.g., Subutex[®]) or buprenorphine/naloxone (e.g., Suboxone[®]; n=10)
- Methadone (n=10)
- Controls (n=2)

Aim 1: Buprenorphine group (n=10):

- **Inclusion criteria for buprenorphine group includes:**
 - Age 18-65.
 - A prescription for sublingual buprenorphine or buprenorphine/naloxone at dose \geq 16mg/4mg
 - Taken buprenorphine or buprenorphine/naloxone as prescribed in the last 7 days.
- **Exclusion criteria for buprenorphine group includes:**
 - Age <18 or >65.
 - A condition preventing or complicating ISF collection. Conditions may include dermatological (skin) condition, immunodeficiency, recent blood donation, anemia, cancer, congestive heart failure, HIV, Hepatitis C [HCV], or tuberculosis [TB].
 - Any active severe depression (e.g., suicidal ideation) or mania symptoms.

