 - Lactation, pregnancy, or intending to become pregnant during the course of the study.
 - Alcohol use in the past 7 days.
 - Illicit substance use in past 7 days (e.g., heroin, methamphetamines).
 - Under a conservatorship.

Aim 2: Methadone group (n=10):

- **Inclusion criteria for methadone group includes:**
 - Age 18-65.
 - A prescription for liquid methadone at dose \geq 60mg.
 - Taken methadone as prescribed in the last 7 days.
- **Exclusion criteria for methadone group includes:**
 - Age <18 or >65.
 - A condition preventing or complicating ISF collection. Conditions may include dermatological (skin) condition, immunodeficiency, recent blood donation, anemia, cancer, congestive heart failure, HIV, HCV, or TB. Any active severe depression (e.g., suicidal ideation) or mania symptoms.
 - Lactation, pregnancy, or intending to become pregnant during the course of the study.
 - Alcohol use in the past 7 days.
 - Illicit substance use in past 7 days (e.g., heroin, methamphetamines).
 - Under a conservatorship.

Aim 3: Establish correspondence between ISF & Blood (n=22):

- **Inclusion criteria for this group includes:**
 - Age 18-65.
 - A prescription for buprenorphine at dose \geq 16 mg/4mg, a prescription for buprenorphine/naloxone at dose \geq 16 mg/4mg, a prescription for methadone at dose \geq 60mg, or part of the control group.
 - Taken buprenorphine, buprenorphine/naloxone, or methadone as prescribed in the last 7 days, or part of the control group.

- **Exclusion criteria for this group includes:**

- Age <18 or >65.
- A condition preventing or complicating ISF collection. Conditions may include schizophrenia, bipolar, depression, dermatological (skin) condition, immunodeficiency, recent blood donation, anemia, cancer, congestive heart failure, HIV, HCV, or TB.
- Any active severe depression (e.g., suicidal ideation) or mania symptoms.
- Lactation, pregnancy, or intending to become pregnant during the course of the study.
- Alcohol use in the past 7 days.
- Illicit substance use in past 7 days (e.g., heroin, methamphetamines).
- Under a conservatorship.

Control Group (n=2):

- **Inclusion criteria for control group includes:**

- Age 18-65.

- **Exclusion criteria for control group includes:**

- Age <18 or >65
- Prescription for opioid medications (e.g., buprenorphine, buprenorphine/naloxone, methadone)
- Have not taken any opioids agonist medications (e.g., buprenorphine, buprenorphine/naloxone, methadone) in the last 7 days.

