- A condition preventing or complicating ISF collection. Conditions may include schizophrenia, bipolar, depression, dermatological (skin) condition, immunodeficiency, recent blood donation, anemia, cancer, congestive heart failure, HIV, HCV, or TB.
- Any active severe depression (e.g., suicidal ideation) or mania symptoms.
- Lactation, pregnancy, or intending to become pregnant during the course of the study.
- Alcohol use in the past 7 days.
- Illicit substance use in past 7 days (e.g., heroin, methamphetamines).
- Under a conservatorship.

B. Sex

Equal inclusion of both men (n= 11) and women (n= 11) will be included to ensure the equitable sharing of both the potential risks, and the potential benefits that may result from this research. Women of childbearing potential are eligible to participate in this study. Acceptable methods of birth control include abstinence, meaning a total lack of any sexual activity, as well as the use of oral contraceptives (the “pill”), contraceptive injections, intrauterine device, double-barrier method (diaphragm or condom + spermicidal cream), contraceptive patch, or male partner sterilization. Pregnant women will not be included.

C. Racial/Ethnic Origin

There will be no racial/ethnic enrollment restrictions in this pilot study.

D. Vulnerable Populations

Vulnerable populations such as pregnant women, children, fetuses, wards of the state, severely cognitively impaired individuals, as well as prisoners and institutionalized individuals will not be included in this pilot study.

E. Age

Subjects under the age of 18 will not be included in this study. Older adults are known to metabolize substances differently, as such those over 65 will also not be included in this study.

F. Total Number of Participants to be Enrolled

As seen in a similar study sampling ISF to identify and compare clinically relevant and distinct biomarker composition, up to 22 subjects will be enrolled in this study.¹⁰

STUDY DESIGN / METHODS / PROCEDURES

We will conduct a non-randomized, non-blinded, feasibility study at a single center in the United States. The study will include a total of 10 male and 10 female adults (ages 18–65) who have a prescription for buprenorphine, buprenorphine/naloxone, or methadone and 1 male and 1 female adult control participants (total n=22).

A. Summary of the Research Design

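### Does the separate Aim 3 exclusion list, which names three psychiatric conditions that the Aim 1 and Aim 2 lists do not, leave eligibility undefined or shrink the ISF–blood comparison?

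*Protocol*

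**What the plan says.** Under PARTICIPANT SELECTION, the heading of the inclusion and exclusion criteria announces "3 groups (total n=22"): buprenorphine 10, methadone 10, controls 2. Four sets of criteria follow, one each for Aim 1 (buprenorphine), Aim 2 (methadone), Aim 3 and the control group. Aim 3 is introduced as "Aim 3: Establish correspondence between ISF & Blood (n=22"), and its inclusion lines admit buprenorphine patients, methadone patients and controls.

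All four sets exclude people with a condition that would prevent or complicate ISF collection, and all four then offer examples. For Aim 1 the examples begin "Conditions may include dermatological (skin) condition, immunodeficiency" and contain no psychiatric diagnosis; Aim 2 gives the same conditions. For Aim 3 they begin "Conditions may include schizophrenia, bipolar, depression, dermatological (skin) condition", and the control list opens the same way.

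Every set also excludes severe active depression and manic symptoms. In Aim 2 that line has run into the end of the condition list: "HIV, HCV, or TB. Any active severe depression (e.g., suicidal ideation) or mania symptoms".

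The inclusion lines differ slightly too. Aim 1 asks for "A prescription for sublingual buprenorphine or buprenorphine/naloxone at dose" and Aim 2 for "A prescription for liquid methadone at dose", each with a minimum; Aim 3 repeats the minimum doses but not the words sublingual and liquid.

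**The concern.** Aim 3 is an analysis question put to the same 22 people, yet it is written as if it were a fourth group with its own entry rules. A medicated patient with schizophrenia, or with bipolar disorder or depression that is neither active nor severe, matches a named example under Aim 3 but nothing named under Aim 1 or 2. The screening and consent paragraphs in the Summary of the Research Design speak of the inclusion and exclusion criteria without saying which list applies to such a patient.

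The criteria could then be read to mean that this patient qualifies for the drug-detection aims and not for the ISF–blood comparison. If that split occurred, Aim 3 would fall below its stated 22, one person at a time, in a study that is already small. The Aim 3 list cannot simply replace the other two, because it omits the formulation words. Depression also appears in Aim 3 without a severity limit, beside a line that does carry one.

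**Working it through.** **Head count.** The inputs are the group sizes in the inclusion and exclusion criteria. 10 + 10 + 2 = 22, which reproduces the stated total and the stated Aim 3 size. Participants in Aim 3 alone: 22 − 22 = 0. Participants under both a medication-group list and the Aim 3 list: 10 + 10 = 20, or 20/22 = 91%.

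**Example conditions compared.**

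| List | Somatic examples | Psychiatric examples | Total |
|---|---|---|---|
| Aim 1 | 9 | 0 | 9 |
| Aim 2 | 9 | 0 | 9 |
| Aim 3 | 9 | 3 | 12 |
| Controls | 9 | 3 | 12 |

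The 9 are the same throughout: skin condition, immunodeficiency, recent blood donation, anemia, cancer, congestive heart failure, HIV, HCV and TB. The difference is exactly schizophrenia, bipolar and depression. For the 2 controls the two applicable condition lists agree, so only the 20 medicated participants are touched.

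**What the criterion requires.** In each list the rule is that the condition hinders ISF collection, and the named conditions are things that may do so. A medicated patient whose schizophrenia hinders collection can be excluded under Aim 1 or 2 although it is not named there. One whose condition does not hinder collection is not automatically excluded under Aim 3. The examples differ as guidance; the rule does not.

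**Can both lists be applied together?** Yes.
- Buprenorphine: the Aim 1 inclusion line (sublingual, at or above the stated minimum) combined with the Aim 3 line (same minimum, no formulation) gives back the Aim 1 line.
- Methadone: the Aim 2 line (liquid, at or above the stated minimum) combined with the Aim 3 line gives back the Aim 2 line.
- Exclusions: the 9 examples combined with the 12 give the 12.

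The missing formulation words therefore do no harm, since the narrower group wording still binds.

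**Is there a route into Aim 1 or 2 but not Aim 3?** If k medicated patients were kept for Aim 1 or 2 and dropped from Aim 3, Aim 3 would have 22 − k. The Protocol provides no step that makes k greater than 0. The Summary of the Research Design schedules blood and ISF before the dose and again at the expected peak for every medicated participant, with matching collections for controls. Analysis of Study Results takes ISF and blood from up to 22 participants, without a subset.

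**Effect under each reading.**
- Shorter lists as the working guide: those enrolled are scheduled to give both fluids, so Aim 3 covers everyone enrolled.
- Longer list, or both lists together: a patient judged ineligible is never enrolled, so Aim 3 again covers everyone enrolled. The target is a ceiling (up to 22, in Total Number of Participants to be Enrolled), and another patient can be recruited.

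Under either reading, each participant's ISF is compared with that participant's own blood.

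**The two depression lines.** One gives depression as a possible obstacle to ISF collection; the other excludes severe active depression outright. They are separate criteria and can stand side by side.

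**The case for a change.** The best case for a change is that eligibility criteria belong in the protocol and should give one answer. The examples are the only visible guide to a broad criterion, and someone screening from the Aim 1 list, which is wholly somatic, has little reason to think of psychiatric diagnoses. Nothing states that the lists are cumulative. If the longer list governs, the lists headed as belonging to the buprenorphine and methadone groups are incomplete. Aligning them would cost only wording.

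Much of this stands as a comment on drafting. The lists are uneven, and two screeners could treat the same patient differently. It does not reach the study's results. Applying both lists is the natural course for someone who belongs to both a medication group and Aim 3, and it settles every mismatch described. Screening also uses questions in supplemental material that is not shown, and these may already settle what is asked of whom. Nor is the screening call the only check: medical history is collected after consent, and urine tests at the visit can still lead to discharge. Aligned wording would leave the sponsor to decide which conditions to name, so no result can be said to improve. Finally, an aim that uses all enrolled participants is ordinary and is not a fault in itself.

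**Conclusion.** The mismatch is real but clerical: 3 of the 12 examples in the Aim 3 list are absent from the Aim 1 and Aim 2 lists, bearing on 20 of 22 participants. It changes no stated number, introduces no identifiable bias, and leaves the detection aims and the ISF–blood comparison sound. The feared loss from Aim 3 depends on a split between aims that the Protocol nowhere provides for, and the document gives no basis for estimating how many patients have one of the three conditions.

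This conclusion assumes that the examples are read as illustrations of one common criterion, that participants in both a medication group and Aim 3 are held to both lists, and that all enrolled participants follow the single sampling schedule. The text supports the first and third directly; the second is the sensible reading where the text is silent. No change to the plan is called for. Whether to align the example lists when the text is next edited is for the sponsor, and this review takes no view on which conditions should be named.

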Subject Recruitment Strategy: Up to 18 adults ages 18-65 years of age will be recruited to participate in this study. Subjects will be recruited from addiction medicine clinics through provider referrals (e.g., El Dorado Community Service Centers). Human subjects research will be performed at Synergy Research Centers (<https://www.synergyresearchcenters.com>) in San Diego which is a well-established clinical trial company that provides appropriate staff and facilities to conduct this study.

Study Procedures: The study consists of a 1) pre-screening phone call, 2) online assessment, 3) an in-person baseline clinical visit which will include a urine toxicology test, urine pregnancy test, pre blood sample, ISF extractions, and post blood sample, and 4) a post-ISF extraction follow-up call approximately 2 days after baseline visit. As such, there will only be one in-person visit.

- **Screening (up to 10 minutes)**

- Potentially eligible subjects will be identified by the research team and clinical staff through addiction medicine clinic referrals. The screening process may occur in-person or online. However, subjects will use an online screening process in both situations.
- Study eligibility will be conducted by the clinical research coordinator (CRC). See the supplemental material for specific questions.

- **Consent (up to 10-30 minutes):**

- If the potential subjects meet the inclusion criteria, does not meet the exclusion criteria, and agrees to learn more about the study, the CRC will send the study consent document link via an online Good Clinical Practice (GCP) compliant program to the subject for review.
- The CRC will walk the subjects through the consent and answer any questions the subject might have. As such, there will be no paper consents.

- **Initial questionnaire (up to 15-30 minutes):**

- If the potential subjects agree to participate as indicated by their online signature on the consent, they will be assigned a computer-generated Subject ID code and will be asked to complete the online baseline questionnaire in a GCP compliant data collection program (see the supplemental material for specific questions).
 - Demographics (e.g., age, sex, race, ethnicity)
 - Past and current diseases or medical conditions
 - Previous operations or medical procedures
 - Any medicines, vitamins, minerals, and herbal remedies that the person is currently taking
 - Diet and exercise habits
 - Tobacco, alcohol and other substance use history

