- i. ISF will be collected by a board-certified physician with procedural skills, training, and familiarity with ISF collection. ISF collection will follow collection practices as described below and applied elsewhere.¹⁰ The first ISF collection will occur immediately before the participant takes their prescribed medication. A subsequent collection will occur at the medication peak (e.g., 2-4 hours after medication administration; see below).
 - ii. ISF will be collected from the surface of the right or left arm (subject preference).
 - iii. The subject will be prepared for the ISF collections using standard clean working techniques (e.g., prepped and draped).
 - iv. The procedures will involve covering the skin with a transparent film skin dressing (e.g., Tegaderm) containing a 1-cm-diameter opening where microneedle treatment will be performed.
 - v. A minimally invasive microneedle array will be used in conjunction with a standard vacuum pump. Microneedles (without the patch) will be inserted and removed multiple times (~10) to collect about $\geq 1 \mu\text{l}$ of ISF. This approach has been well tolerated with faint visual evidence of micropores in the skin in a previous study.¹⁰ A standard vacuum pump will then be administered at -50 kPa at room temperature for 20 min to draw out the ISF. Skin appearance should remain largely unchanged and result in a swift recovery as seen in a previous study.¹⁰ Commercially available gauze will then be used to collect the ISF from the surface of the skin.

- vi. After the ISF collection is complete, a sterile bandage covering will be supplied to the area.
- vii. Subjects will be monitored after each ISF collection for up to 30 minutes and be asked to report their tolerability, pain, and experience. Their responses will be documented in a secure GCP certified online storage medium.
- viii. This process will also occur for the control group. Because the control group will not be administered a medication, the timing of the blood and ISF collection will occur after physical assessment and 2-4 hours after the first collection.

d. Prescribed dose of medication (5 minutes)

- i. Participants will be asked to take their prescribed oral medication at the study site. Study personnel may observe.

e. Second Microneedle ISF collection (up to 1 hour)

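### A control-group exclusion criterion is worded backwards: as written it bars people who have not recently taken an opioid agonist

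*Protocol*

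**What the plan says.** Under Participant Selection, B. Inclusion and Exclusion Criteria, the Control Group (n=2) has one inclusion criterion, age 18 to 65. Its exclusion list is headed "Exclusion criteria for control group includes". One entry in that list reads "Have not taken any opioids agonist medications (e.g., buprenorphine, buprenorphine/naloxone, methadone) in the last 7 days". The entry just before it excludes people with an opioid prescription, and a later entry excludes illicit substance use in the past 7 days.

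The consent step, under A. Summary of the Research Design, shows how the lists are applied. The consent link goes out "If the potential subjects meet the inclusion criteria, does not meet the exclusion criteria, and agrees to learn more about the study".

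Two other places show what kind of control is meant:

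- The Aim 3 inclusion criteria require a participant to have "Taken buprenorphine, buprenorphine/naloxone, or methadone as prescribed in the last 7 days, or part of the control group".
- Item viii of the first microneedle ISF collection sets the controls' sampling times separately, "Because the control group will not be administered a medication".

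**The concern.** Every other entry in the control exclusion list names a state that disqualifies a person. This one names the state a control ought to be in. Because a person must meet none of the exclusions, the negated wording shuts out opioid-free volunteers and lets recent opioid-agonist users past that line.

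The control group's eligibility is at stake. These two people supply the only planned samples from participants not taking buprenorphine or methadone. In a study asking whether those drugs can be detected in ISF, their evident use is as a drug-free reference. The protocol describes recruitment only through referrals from addiction medicine clinics, so recent agonist exposure is a real screening question. Whichever way staff act, conduct and text cannot both be right: either almost no control qualifies, or each control enrolled breaches a written criterion.

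**Working it through.** The plan gives no figure to reproduce, so the check is one of logic, followed by a simple count.

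**Inputs.** Three yes/no facts about a candidate control of eligible age, each taken from an entry in the control exclusion list:

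- P: has an opioid prescription (excluded if yes)
- I: illicit substance use in the past 7 days (excluded if yes)
- T: took an opioid agonist in the last 7 days (as written, excluded if **no**)

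**Rule.** A candidate is eligible only if no exclusion is met.

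- As written: eligible = not P, not I, and T.
- As evidently intended: eligible = not P, not I, and not T.

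| P | I | T | As written | As intended |
|---|---|---|---|---|
| no | no | no | excluded | eligible |
| no | no | yes | eligible | excluded |
| no | yes | no | excluded | excluded |
| no | yes | yes | excluded | excluded |
| yes | no | no | excluded | excluded |
| yes | no | yes | excluded | excluded |
| yes | yes | no | excluded | excluded |
| yes | yes | yes | excluded | excluded |

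Each reading admits one of the eight combinations, and they are different ones. Nobody satisfies both. The combination admitted as written is a person who used an opioid agonist with no prescription and whose use does not count as illicit.

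**Why the intended reading is the right one.** The Aim 3 inclusion criteria offer control membership as the alternative to having taken the medication. The sampling procedure says controls receive none. The neighbouring prescription exclusion points the same way.

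**Is the rule stated correctly elsewhere?** Not in the visible text. The control inclusion list contains only age. The illicit-use entry gives heroin and methamphetamines as examples, not buprenorphine or methadone. The urine toxicology list covers heroin, oxycodone and other opiates but names neither study drug. The reversed line is therefore the only control criterion addressing recent use of the drugs being assayed.

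**Size.**

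- Following the text: 22 − 2 = 20 participants for Aim 3.
- Following the intent: 2 of 2 controls breach a written criterion; 2/22 = 9.1% of participants.
- Samples per person: 2 ISF + 2 blood = 4. Controls supply 2 × 4 = 8 of 22 × 4 = 88, the same 9.1%.

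**The case against.** The strongest reply is that nobody reading the whole protocol would misunderstand it. The surrounding criteria and procedures make the intent obvious, so the likely result is a formal mismatch and not a lost control group. There are also partial safeguards. The clinic visit may ask about opioid use in the past week, and a positive urine test for a listed non-prescribed substance leads to discharge. The screening questions are held elsewhere ("See the supplemental material for specific questions") and may be worded correctly. Finally, 22 is a ceiling, and two drug-free people add essentially nothing to a correlation of drug levels between ISF and blood, so the fall to 20 says little about what Aim 3 would lose.

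Much of this stands. A misreading is unlikely, the headcounts are upper limits, and the controls matter as a drug-free reference more than for the correlation. None of it corrects the criterion. If staff read it as intended, both controls are enrolled contrary to the written list. The safeguards do not name buprenorphine or methadone.

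It can also be objected that the protocol does not say whether non-prescribed buprenorphine or methadone counts as illicit use. That is fair, but it does not help the text. If such use is not illicit, the written list would admit a control who had recently taken the very drugs being measured.

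**Conclusion.** The concern holds. The line has the wrong polarity for the list it stands in and contradicts the protocol's own description of its controls. It affects 2 of up to 22 participants (9.1%) and changes no sample-size or error-rate figure. It should be fixed because it is an operative eligibility rule that no other visible line corrects.

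Two assumptions matter. The statement that practically nobody qualifies as written assumes that taking an opioid agonist without a prescription would largely count as illicit use. The counts assume full enrolment of 22 with all four samples taken per person. Whether the screening questions repeat the error cannot be judged, because they are not in the document.

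**What to change.** Reconcile the control criteria with the rest of the protocol in one of two equivalent ways:

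- keep the line in the exclusion list and remove the negation, so that having taken an opioid agonist in the last 7 days is what excludes a control; or
- move the line, unchanged, to the control inclusion list.

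Then check that the screening questions in the supplemental material apply the same rule.

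The cost is a one-sentence protocol correction submitted to the IRB, plus that check. Visits, samples and sample size are unaffected.

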Unique Protocol ID: 1332356

Brief Title: Assessment of Methadone and Buprenorphine in Interstitial Fluid

Official Title: Interstitial Fluid Collection Validation Study

NCT number : NCT05546229

IRB Protocol document submittal date : July 19 2023

IRB final approval date : August 3 2023

Interstitial Fluid Collection Validation Study
IRB Research Proposal
Protocol #002
July 19, 2022

BACKGROUND INFORMATION

Sponsor: CARI Health, Inc.
PI: [name]
Email address: [contact]
[contact]

INTRODUCTION

A. Type of Research

Pilot Study

B. Purpose/Objective of the Study

This pilot study is an exploratory feasibility study that aims to determine if common medications for opioid use disorder (OUD; i.e., buprenorphine, methadone) and their metabolites (i.e., norbuprenorphine [a metabolite of buprenorphine], buprenorphine-3-glucuronide [B3G; a metabolite in buprenorphine], ethylidene dimethyl diphenyl pyrrolidine [EDDP; a metabolite for methadone]), can be detected in dermal interstitial fluid (ISF). Similar to our previous ISF study approved by WCG IRB and completed in 2021 (IRB Tracking ID 20214878), microliter volumes of ISF from the surface of the skin will be collected from patients with a prescription for each of these medications (buprenorphine n = 10; methadone n = 10) and controls (n=2) using a microneedle patch or minimally invasive microneedle array that may be used in conjunction with a standard vacuum pump. Levels of these medications and their metabolites will then be detected and quantitated in these samples using standard and well-established instrumental analysis for comparison to blood samples.

Aim 1: Detect and quantitate buprenorphine and norbuprenorphine in ISF collected from the surface of the skin using a minimally invasive microneedle array. ISF collected from the surface of the skin will be tested for buprenorphine (i.e., Suboxone®, Subutex®), norbuprenorphine (a metabolite of buprenorphine), and B3G (a metabolite of buprenorphine) using standard instrumental analysis.

Aim 2: Detect and quantitate methadone in ISF collected from the surface of the skin using a minimally invasive microneedle array. ISF collected from the surface of the skin will be tested for methadone and EDDP using standard instrumental analysis.

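### The recruitment paragraph caps the study at 18 adults, but every other head count in the protocol gives 22

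*Protocol*

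**What the plan says.** Only the protocol is at hand. Under Study Design / Methods / Procedures, section A (Summary of the Research Design), the Subject Recruitment Strategy opens with "Up to 18 adults ages 18-65 years of age will be recruited to participate in this study". It names referral from addiction medicine clinics as the route of recruitment.

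The other head counts are these:

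- Introduction, section B (Purpose/Objective of the Study): "buprenorphine n = 10; methadone n = 10) and controls (n=2".
- Participant Selection, Inclusion and Exclusion Criteria, heading: "3 groups (total n=22".
- The group headings in the same section: "Buprenorphine group (n=10", "Methadone group (n=10" and "Control Group (n=2".
- The Aim 3 heading in the same section: "Establish correspondence between ISF & Blood (n=22".
- Participant Selection, section B (Sex): "Equal inclusion of both men (n= 11) and women (n= 11".
- Participant Selection, section F (Total Number of Participants to be Enrolled): an upper limit of 22.
- Study Design / Methods / Procedures, opening paragraph: 10 men and 10 women on one of the study medications, plus 1 man and 1 woman as controls, with the total given as 22.
- Study Design / Methods / Procedures, section B (Analysis of Study Results): samples from at most 22 participants.

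**The concern.** The recruitment paragraph is the operative instruction on how many people to bring into the study, and its number differs from all the others. The protocol does not explain 18 as an evaluable subset, a patients-only count, an allowance for dropout or anything else.

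A site that followed this paragraph would stop before the three groups were full. A site that followed section F could go past the ceiling in the recruitment paragraph. Each participant undergoes two blood draws and two microneedle collections with suction, so the ceiling should be stated once and without ambiguity. The protocol describes itself as an exploratory feasibility pilot and gives no power or precision calculation, so no inferential claim is at risk.

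**Working it through.** **Reproducing the plan's own total.** The stated counts give 22 in three ways:

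- By group (Purpose/Objective; group headings): 10 + 10 + 2 = 22.
- By sex (section B, Sex): 11 + 11 = 22.
- By medication status and sex (opening paragraph of Study Design): 10 + 10 + 1 + 1 = 22.

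All three agree with section F, the Aim 3 heading and the analysis section.

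**Can 18 be a subset?** These are all the sums that can be formed from one or more of the stated cells:

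| Cells | Possible sums |
|---|---|
| Groups {10, 10, 2} | 2, 10, 12, 20, 22 |
| Medication status by sex {10, 10, 1, 1} | 1, 2, 10, 11, 12, 20, 21, 22 |
| Sex {11, 11} | 11, 22 |

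18 is in none of the rows.

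**Other readings of 18:**

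- *Medicated participants only.* The design paragraph fixes these at 10 + 10 = 20.
- *Recruited as distinct from enrolled.* People must be recruited before they can be enrolled, so the number recruited cannot be the smaller of the two.
- *Allowance for losses.* The protocol states no dropout rate. It does discharge consented participants who have a positive urine toxicology or pregnancy test at the visit. Such losses push the number recruited above the number sampled, whereas 18 lies below 22.
- *Clinic referrals only, with others found elsewhere.* The sentence is not limited to one source, and the paragraph names no other. Even on this reading, 18 referrals could not fill 20 medicated places.

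**Size of the gap:**

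- Against the full total: 22 − 18 = 4, and 4/22 = 18.2%.
- Against the medicated places: 20 − 18 = 2, and 2/20 = 10%.

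**The case against.** The strongest reply concerns weight. A section headed as the total to be enrolled says 22, the design paragraph just before the recruitment text repeats it, and the remaining counts agree. Most readers would take 22 as the number and 18 as a leftover, so the chance that a site really stops at 18 is low. That is fair, and it is why the point is a small reconciliation.

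A second reply is that the recruitment sentence, section F and the analysis section all state upper limits. Enrolling 18 or fewer would breach none of them, so these sentences alone show only ceilings that do not match. That is also correct. The firm conflict is with the counts stated without such a qualifier: the 10/10/2 groups, the 11/11 sex split, and the design paragraph's 20 medicated participants plus 2 controls. A cap of 18 makes all of these unattainable.

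Third, the protocol gives IRB submission and approval dates but not the number of participants approved, so nothing can be said about which figure the IRB accepted. What stands is that the proposal submitted to it contains two ceilings.

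Finally, no sum in the protocol is wrong. This is one inconsistent number, and the percentages above describe a shortfall that would arise only if that number were obeyed.

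**Conclusion.** The point holds. The recruitment ceiling of 18 is wrong as written, or else every other head count is. The gap is 4 of 22 participants (18.2%), or 2 of the 20 medicated places (10%). The weight of the document favours 22, so 18 is probably a slip, but only the sponsor can confirm that.

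The conclusion rests on exact counts stated in the protocol and on one assumption: that recruited keeps its ordinary sense, so that nobody is enrolled without having been recruited. Eligibility, procedures, sampling times and analysis are unaffected. It should be fixed because the error is certain, it sits in an operative section, and it concerns how many people may be exposed to the procedures.

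**What to change.** If 22 is intended, change 18 to 22 in the first sentence of the Subject Recruitment Strategy and add the breakdown in brackets: 10 buprenorphine, 10 methadone, 2 controls. The cost is one number and a short breakdown in one sentence, with no change to procedures or analysis.

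If 18 is the true ceiling, restate the group sizes in Purpose/Objective and in the group headings, the totals of 22 in the eligibility and Aim 3 headings, the sex split, section F, the opening design paragraph and the analysis section. That means more edits, and it requires a decision on how 18 divides among the three groups and between the sexes.
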